14.5 Safety

The assessment of safety will be based mainly on the frequency of AEs that are treatmentemergent. Formal statistical tests will not be conducted for differences in safety parameters between treatment groups.

The incidence of all treatment-emergent AEs will be after grouping by body system and preferred term. For each preferred term and summarized over each body system overall, the table will present the number of patients in each treatment group in whom the event occurred and the rate (%) of occurrence. The incidence of all suspected-drug-related AEs will be tabulated similarly. The incidence of all treatment-emergent AEs will also be tabulated by severity categories. The summary of all AEs by treatment groups will also be presented within subgroups by sex, age and race.

Safety will also be summarized with respect to vital signs and laboratory safety parameters as mean levels by visit and change from baseline. Laboratory values will be further summarized with shift tables. Abnormal observations on physical exams will be listed

CRMB	Trial Substance:	Esflurbiprofen Hydrogel Patch	Study No.: TK-254R-0201 EudraCT No.: 2020-005165-14
	Short Title:	Local symptomatic and short-term treatment of pain in acute strains, sprains or bruises of the extremities following blunt trauma	Sponsor: TEIKOKU SEIYAKU CO LTD.

14.5.1 Adverse events

Adverse events will be coded according to MedDRA, Version 24.0.

The incidence of all treatment-emergent AEs will be tabulated after grouping by body system and preferred term. For each preferred term and summarized over each body system overall, the table will present the number of patients in each treatment group in whom the event occurred and the rate (%) of occurrence. The incidence of all suspected-drug-related AEs will be tabulated similarly. The incidence of all treatment-emergent AEs will also be tabulated by severity categories.

14.5.2 Other Variables Related to Safety

Summary statistics for the absolute vital sign value and the changes from baseline will be presented using n, mean, standard deviation, median, minimum, and maximum.

Abnormal observations on physical examinations will be listed.

Furthermore, weight, pregnancy and assessments of fertility data will only be listed.

Local tolerability assessment will be summarized descriptively by visit.

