Study Objectives To determine efficacy and safety of a Esflurbiprofen Hy compared to placebo in patients with acute strains, sprains the extremities following blunt trauma, e.g. sports injuries.			

	To demonstrate that the Esflurbiprofen Hydrogel Patch is superior to placebo, and that the patch has acceptable local tolerability.			
Study Design Patient Population/Sample size/Study Sites	Randomized (1:1) (stratified by center and 2 subgroups), controlled, double-blind, multi-centric study in parallel groups. The clinical trial population will consist of male or female patients, 18 – 60 years suffering from acute; strains, sprains or bruises of the extremities following blunt trauma, and meeting all clinical trial entry criteria.			
	In order to ensure at least 90 evaluable patients per group, up to 200 patients will be enrolled (assumes a drop-out-rate of $\leq 10\%$).			
	The study will be performed in Germany in 3 sites. Each site should enroll a minimum of 30 and a maximum of 90 patients.			
Statistical Considerations	 enroll a minimum of 30 and a maximum of 90 patients. Samplesize The calculation of 90 per treatment group is based on the following assumptions and considerations: Primary efficacy outcome is the change from baseline for POM 72 hours after initiating treatment. Two-sided t-test situation with α = 5%. Assuming SD = 20 mm, the sample size provides approximate 80% power to detect a difference of 10 mm between two treatmer groups if 64 patients per group are analysed. However, the sample size will be stipulated to n=90 per group i order to power also the two subgroup comparisons. Moreover, the sample size will be a total of 200 patients becaus a dropout-rate of approximately 10 % is taken into account 			

Analysis

Analysis-of-covariance for primary variable with baseline as covariate and treatment, center and subgroup as factors. An a priori ordered testing procedure controlling the multiple α -level of 5 % will be carried out:

1) $H_{o:} \mu_E = \mu_P \text{ vs. } H_1: \mu_{E \neq} \mu_P.$

In case of a significant result for this first hypothesis two further hypotheses regarding the subgroups "sprains" and "contusions" will be

Teikoku Chemical Co. L Clinical Study Protocol :	td TK-254R-0201	Confidential Final Version 3.0	Page 11
	then be also teste model to the 5 %	ed by means of the same baselir level.	ne adjusted ANCOVA

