Teikoku Chemical Co. Ltd Clinical Study Protocol : TK-254R-0201

Documentation of use of rescue medication, if needed (diary check).

- \square Record changes in the use of concomitant medication (section 6.5.6).
- \square Record information on AEs (section 8.1).
- \Box Spontaneous pain intensity, pain at rest (PAR) (section 7.5.1)
- \Box Injury site pain-on-movement (POM) (section 7.5.1).
- □ Visit 4: Global efficacy assessments (GEA) by patient and investigator (section 7.5.1).
- \Box Adhesive power of patch (section 7.5.1).
- □ Local tolerability assessment (except V2).

Visit 5 (72h \pm 4 h)

- \Box Apply next dose of study medication.
- □ Count used/unused patches & collect used patches.
- □ Check for last intake of rescue medication no later than 6 hours prior to Visit.
- □ Documentation of use of rescue medication
- \square Record changes in the use of concomitant medication (section 6.5.6).
- \square Record information on AEs (section 8.1).
- □ Spontaneous pain intensity, pain at rest (PAR) (section 7.5.1)
- \Box Injury site pain-on-movement (POM) (section 7.5.1).
- \Box Global efficacy assessments (GEA) by patient and investigator (section 7.5.1).
- Responder rate 1 (number of patients achieving 50% reduction from baseline in the VAS score for POM)
- \Box Adhesive power of patch (section 7.5.1).
- □ Local tolerability assessment.

Visit 6 (96h+4h)

- □ Apply next dose of study medication.
- □ Count used/unused patches and collect used patches.
- \Box Use of rescue medication.
- \square Record changes in the use of concomitant medication (section 6.5.6).
- \square Record information on AEs (section 8.1).
- \Box Spontaneous pain intensity, pain at rest (PAR) (section 7.5.1).
- \Box Injury site pain-on-movement (POM) (section 7.5.1).

- \Box Adhesive power of patch (section 7.5.1).
- □ Local tolerability assessment.
- □ Dispense patient card (section 6.5.7) and diary (section 6.5.8) and instruct patient about appropriate use.
- Dispense three patches to the patient.
- \Box The patient is instructed on the method and time of application of study drug (section 6.5.4).

Visit 7 (Day 8 ± 2 days) - Final visit

Procedures for this visit are also to be completed if the patient terminates the study prematurely.

- \Box Count used/unused patches and collect used patches.
- \square Record changes in the use of concomitant medication (section 6.5.6).
- \Box Record information on AEs (section 8.1).

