8.1 Adverse events

An adverse event (AE) is the appearance or worsening of any undesirable sign, symptom, or medical condition occurring after starting the study drug even if the event is not considered to be related to study drug. Study drug includes the investigational drug under evaluation and the comparator drug or placebo that is given during any phase of the study. Medical conditions/diseases present before starting study drug are only considered adverse events if they worsen after starting study drug

The occurrence of adverse events should be sought by non-directive questioning of the patient at each visit during the study. Adverse events also may be detected when they are volunteered

by the patient during or between visits or through physical examination, , or other assessments. All adverse events must be recorded on the Adverse Events CRF with the following information:

- 1. the severity grade (mild, moderate, severe)
- 2. its relationship to the study drug(s) (suspected/not suspected)
- 3. its duration (start and end dates or if continuing at final exam)
- 4. whether it constitutes a serious adverse event (SAE)

An SAE is defined as an event which:

- \Box is fatal or life-threatening
- □ results in persistent or significant disability/incapacity
- □ constitutes a congenital anomaly/birth defect
- □ requires inpatient hospitalization or prolongation of existing hospitalization, unless hospitalization is for:
 - o elective or pre-planned treatment for a pre-existing condition that is unrelated to the indication under study and has not worsened since the start of study drug
 - o treatment on an emergency outpatient basis for an event not fulfilling any of the definitions of a SAE given above and not resulting in hospital admission
 - o social reasons or respite care in the absence of any deterioration in the patient's general condition
- □ is medically significant, i.e., defined as an event that jeopardizes the patient or may require medical or surgical intervention to prevent one of the outcomes listed above.

Unlike routine safety assessments, SAEs are monitored continuously and have special reporting requirements.

All AEs and SAEs will be recorded, including their severity, their duration and relationship to study drug.

All adverse events should be treated appropriately. Treatment may include one or more of the following:

- \Box no action taken (i.e., further observation only);
- □ study drug dosage temporarily interrupted;

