5.2 Safety variables

The following parameters are recorded to assess the safety of the study drug:

- Adverse events (AEs). AEs will be documented at Visit 2 to Visit 7.
- Vital signs. Pulse rate (bpm) and blood pressure (BPs, BPd (mmHg) will be documented at the Baseline Visit (Visit 1) and Final Visit (Visit 7)).
- General physical examination.

Physical examination will be performed at Visit 1 (randomization visit) and at Visit 7 (final visit), as well as when judged necessary by the Investigator. Examination will include: general condition, dermatologic, eyes, ears, nose, throat, neck, thyroid, heart, respiratory system, abdomen, kidneys, skeletal system, extremities, lymphatic system, CNS, neurological conditions and other (to be specified).

• Height and weight.

Height in centimeters (cm, without shoes) and body weight (kg, in indoor clothing, but without shoes) will be measured at Visit 1. Body weight only will also be measured at Visit 7.

- Pregnancy and assessments of fertility. All women of child-bearing potential (WOCBP) and postmenopausal women who are not surgically sterile will have a urine pregnancy test with a dipstick at Visit 1 (Randomization Visit) at Visit 7 (Final Visit).
- Local tolerability

Local tolerability will be assessed by the Investigator according to the following numerical scale at Visits 3 to 7:

- 0: No evidence of irritation
- 1: Minimal erythema, barely perceptible
- 2: Definite erythema, readily visible; minimal edema or papular response
- 3: Erythema and papules
- 4: Definite edema
- 5: Erythema, edema, and papules
- 6: Vesicular eruption
- 7: Strong reaction spreading beyond test site

CRMB	Trial Substance:	Esflurbiprofen Hydrogel Patch	Study No.: TK-254R-0201 EudraCT No.: 2020-005165-14
	Short Title:	Local symptomatic and short-term treatment of pain in acute strains, sprains or bruises of the extremities following blunt trauma	Sponsor: TEIKOKU SEIYAKU CO LTD.

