5.5.1 Schedule of assessments

The following table shows the Assessment Schedule of the clinical trial.

CRMB	Trial Substance:	Esflurbiprofen Hydrogel Patch	Study No.: EudraCT No.:	TK-254R-0201 2020-005165-14
	Short Title:	Local symptomatic and short-term treatment of pain in acute strains, sprains or bruises of the extremities following blunt trauma		KU SEIYAKU CO LTD.

Randomization	V2	V3	V4	V5	V6	Final visit ³ (V7)
	1 08 2	2	2	1	5	7, 8 or 9
-		-	-		•	7d (± 1d)
	$1211(\pm 1)$	2411 (±2)	4011 (±4)	72II (±4)	90II(±4)	$7a (\pm 1a)$
						X
X						X
Х	Х	Х	Х	X	Х	x
Х	х	х	х	X	Х	X
х						х
	х	х	х	х	х	х
		х	х	х	х	х
х	х	х	х	х	х	х
х						
х					х	
					х	х
х		х	х	х	х	
х						
	х	х	х	х	х	х
	х	х	х	х	х	x
	х	х	х	х	х	х
	х	х	х	x	х	x
			х	х		x
						x
					х	
	X X X X X X X X X X X X X X X X X X X	1 1 or 2 0h 12h (±1) x x <tr< td="">I I or 2 2 0h $12h (\pm 1)$ $24h (\pm 2)$ x x x x x x x x x x	I I or 2 2 3 0h $12h (\pm 1)$ $24h (\pm 2)$ $48h (\pm 4)$ x x x x x x x x x x x x x x x x x x x x x x x x x x x x x x x x x x x x x x x x x x x x x x x x x x x x x x x x x x x x x x x x x x	I I or 2 2 3 4 0h $12h (\pm 1)$ $24h (\pm 2)$ $48h (\pm 4)$ $72h (\pm 4)$ x x x x x x x X X X X X x X X X X X x X X X X X x X X X X X x X X X X X x X X X X X x X X X X X x X X X X X x X X X X X	I I or 2 2 3 4 5 0h 12h (±1) 24h (±2) 48h (±4) 72h (±4) 96h(±4) x x x x	</tr<>	I I or 2 2 0h $12h (\pm 1)$ $24h (\pm 2)$ x x x x x x x x x x	I I or 2 2 3 0h $12h (\pm 1)$ $24h (\pm 2)$ $48h (\pm 4)$ x x x x x x x x x x x x x x x x x x x x x x x x x x x x x x x x x x x x x x x x x x x x x x x x x x x x x x x x x x x x x x x x x x	I I or 2 2 3 4 0h $12h (\pm 1)$ $24h (\pm 2)$ $48h (\pm 4)$ $72h (\pm 4)$ x x x x x x x X X X X X x X X X X X x X X X X X x X X X X X x X X X X X x X X X X X x X X X X X x X X X X X x X X X X X	I I or 2 2 3 4 5 0h 12h (±1) 24h (±2) 48h (±4) 72h (±4) 96h(±4) x x x x

¹Female patients only; ²Patients will be given pouch containing IMP to take home in case of need to replace a detached patch. Patients bring IMP with them to each subsequent clinic visit. Patient apply patches themselves at 120h and 144h. ³A final visit will be conducted on all patients, including cases of early termination or withdrawal of consent.

CRMB	Trial Substance:	Esflurbiprofen Hydrogel Patch	Study No.: EudraCT No.:	TK-254R-0201 2020-005165-14

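### Local tolerability is summarised only visit by visit, so its own tables cannot show how many patients ever had a skin reaction or how bad the worst one was

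*SAP*

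**What the plan says.** The Study Objectives in the Protocol Synopsis include showing "that the patch has acceptable local tolerability".

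SAP 5.2 defines the measurement: "Local tolerability will be assessed by the Investigator according to the following numerical scale at Visits 3 to 7". The scale has eight grades, from 0 (no irritation) to 7 (a strong reaction spreading beyond the test site). No score is taken at Visit 1 or Visit 2.

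SAP 14.5.2 gives the full analysis of the scale in one sentence: "Local tolerability assessment will be summarized descriptively by visit". It names no treatment arm, population or denominator, and no worst or any-time score.

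Three other places bear on the point:

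- **Adverse events.** SAP 14.5.1 counts treatment-emergent events per patient. For each preferred term the "table will present the number of patients in each treatment group in whom the event occurred and the rate (%) of occurrence".
- **Early termination.** Under Visit 7, Protocol section 7 states: "Procedures for this visit are also to be completed if the patient terminates the study prematurely". Local tolerability is among those procedures. Footnote 3 to the SAP 5.5.1 schedule says that a final visit is "conducted on all patients, including cases of early termination or withdrawal of consent". Protocol 6.5.9 allows up to one week after study drug is stopped for these evaluations.
- **Missing data.** SAP 14.8 carries values forward after premature termination, and carries the baseline value forward if the reason was a suspected drug-related adverse event. It does not say whether tolerability is covered.

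**The concern.** A reader judging a patch will ask two things about the skin: what proportion of patients reacted in each arm, and how severe the worst reaction was. Five separate by-visit distributions answer neither. The same few patients may be affected every time, or different patients at each visit, and the tables would look the same.

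The scale is the one standardised, investigator-scored measure of local tolerability in the trial. If it yields no per-patient result, the conclusion on that aim must lean on the adverse event tables. Those capture only reactions that each site chose to record as events, and nothing in either document ties a score to an adverse event record.

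The by-visit tables are also not fully defined for patients who stop early, the group in which irritation matters most.

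**Working it through.** The documents give no reaction rate and no tolerability target, so there is no planned figure to reproduce. The rates below are assumptions for illustration.

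**1. What by-visit counts can and cannot identify**

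Inputs: 5 scored visits (SAP 5.2) and N = 100 per arm (SAP section 2). The count k at each visit is assumed, and taken as equal across visits.

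- Fewest patients ever affected: k (the same patients each time).
- Most patients ever affected: min(N, 5k) (different patients each time).

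| k per visit (assumed) | Rate shown at each visit | Patients ever affected, of 100 |
|---|---|---|
| 2 | 2% | 2 to 10 |
| 3 | 3% | 3 to 15 |
| 5 | 5% | 5 to 25 |
| 10 | 10% | 10 to 50 |

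For k = 3, the exact (Clopper-Pearson) 95% intervals at the two ends are 0.6% to 8.5% for 3/100 and 8.6% to 23.5% for 15/100. Identical by-visit tables are compatible with both.

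**2. Whether the adverse event tables fill the gap**

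Protocol 8.1 is broad: "An adverse event (AE) is the appearance or worsening of any undesirable sign, symptom, or medical condition occurring after starting the study drug". It also allows events to be detected through assessments, and all adverse events must be recorded. A visible skin reaction can therefore qualify, and if recorded it is counted once per patient by arm, and again by severity.

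Two links are missing. No score is named as the point at which a reaction becomes an adverse event; grade 1, for example, is barely perceptible erythema. And adverse event severity is mild, moderate or severe, with no mapping to the 0-7 scale. The adverse event tables thus cover part of the question, and the size of that part is unknown.

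**3. Denominators after early stopping**

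A patient who stops should still give one tolerability score at the final visit. Scores for visits between stopping and that visit are not defined. SAP 14.8 is not expressly limited to efficacy. Its counterpart, Protocol 9.7.3, sits in the efficacy section, yet Protocol 7.5.1 lists local tolerability among the clinic efficacy assessments. Carrying a baseline score forward would need a baseline score, and none is taken.

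The choice matters. Assume that 10 of 100 react at Visit 3, s of them stop, the others still react, and those who stopped have no score at the later visit:

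| s | Later visit, observed patients only | Later visit, 0 carried forward as baseline | Ever affected |
|---|---|---|---|
| 2 | 8/98 = 8.2% | 8/100 = 8% | 10/100 |
| 5 | 5/95 = 5.3% | 5/100 = 5% | 10/100 |
| 10 | 0/90 = 0% | 0/100 = 0% | 10/100 |

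This shows what could happen under those readings. The documents do not settle which one applies. A worst-score table is unaffected, because it keeps the Visit 3 score.

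**The case against.** The strongest reply is that the plan already counts affected patients. SAP 14.5 bases safety mainly on adverse event frequency, and a patient who stops for irritation should have an adverse event on record, since permanent discontinuation of study drug is one of the listed actions taken for an event. SAP 14.11 adds reasons for discontinuation, in a summary and a by-subject listing. This stands. A reader might infer from SAP 14.5.2 that no table at all counts patients with a skin reaction, and the documents do not support that. The gap is confined to reactions scored on the scale but not recorded as adverse events, and to the worst grade on the scale.

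A reader might also infer that patients who stop for irritation disappear from later denominators, so that the tables improve as patients leave. That is not established either. Final-visit procedures are required at early termination, visits are re-mapped to the nearest nominal time (SAP 14.2), and SAP 14.8 could be read as imputing the rest. The denominator is unspecified; it is not shown to shrink.

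The upper end of the range in step 1 needs a different set of patients at each visit. That is unlikely when the patch goes back on the same marked site. The true figure may lie nearer the lower end, but the by-visit tables cannot show where.

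Finally, the plan is descriptive on purpose: Phase II, with no formal safety tests. A per-patient table with a confidence interval is still descriptive and does not conflict with that.

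**Conclusion.** The point holds in a limited form. The tolerability tables planned in SAP 14.5.2 cannot give the number of patients ever affected or their worst grade, although acceptable local tolerability is a stated aim. The adverse event tables close the gap only for reactions also recorded as adverse events, and no rule makes that complete. The by-visit denominator after early stopping, and whether SAP 14.8 applies to this score, are left open.

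The size can only be illustrated: under equal counts at five visits, the number ever affected lies between k and 5k, for example 3 to 15 or 5 to 25 of 100. The counts are assumed and the upper bound is an extreme case.

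A cut-off at grade 3 or above, read as moderate or worse, might look natural. Neither document sets one, and the scale is not clearly ordered by severity: grade 4 is edema alone, following erythema with papules at grade 3. Any score of 1 or more, together with the full worst-grade distribution, avoids that choice.

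**What to change.** In SAP 14.5.2:

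1. Add a table of each patient's worst post-baseline local tolerability score, by treatment arm in the safety population, including scores taken at early termination. Show the number and percentage at each grade and with any score of 1 or more. Show patients with no score as a separate row.
2. For any score of 1 or more, give the difference between arms with a 95% confidence interval, labelled descriptive.
3. Keep the by-visit table as supportive, by arm, with the number of patients observed at each visit.
4. State that the carry-forward rules of SAP 14.8 do not apply to this score.

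The table does not depend on how sites decided what to record as an adverse event, so no reporting threshold has to be introduced for it.

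The cost is one extra table from data already collected, with no change to any other analysis. The one downside is presentational: on the same denominator, the per-patient rate will be at least as high as the rate at any single visit.

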14.6 Multi-site study

Individual site results will be presented by means of descriptive statistical methods for the demographical and primary efficacy data. Moreover, the treatment-by-site interaction will be assessed by means of an ANCOVA model for the primary variable and other selected secondary variables.

14.7 Multiplicity

A closed test procedure will be carried out for the primary variable. Therefore, no α -adjustments are necessary. The multiple level of $\alpha = 5$ % is controlled by this procedure.

14.8 Missing data

- If assessments at any visit for Visits 2 (12 h) through Visit 6 (96 h) are missing, they will be imputed as the average of the preceding and the following assessments. Fractional values will be rounded down (including ordered categorical assessments). If assessment at Visit 7 is missing, the last observation will be carried forward.
- If a patient terminates prematurely,
 - all subsequent visits will be imputed by carrying the last non-missing observation forward.
 - for an adverse event suspected to be study-drug-related, then all subsequent visits will be imputed by carrying the baseline observation forward.
 - for lack of efficacy, all subsequent assessments will be imputed as the worst of all documented assessments.
 - for lack of efficacy or for an adverse event suspected to be study-drug-related and does not complete the global assessment of treatment satisfaction, it will be assigned the worst possible score.

CRMB	Trial Substance:	Esflurbiprofen Hydrogel Patch	Study No.: EudraCT No.:	TK-254R-0201 2020-005165-14
	Short Title:	Local symptomatic and short-term treatment of pain in acute strains, sprains or bruises of the extremities following blunt trauma	Sponsor: TEIKO	KU SEIYAKU CO LTD.

- If a patient discontinues for any other reason, missing global assessments at Visit
 7 will be imputed by LOCF from Visit 5 and missing assessments at Visit 5 will not be imputed.
- If a patient assesses efficacy at the site < 6 hours after using rescue medication, imputation will be discussed in the Blind Review Meeting, with consideration given to the frequency of this issue in the database and the elapsed time between rescue and assessment of efficacy.
- If a patient assesses spontaneous pain intensity and spontaneous pain relief at the time of rescue taken because of blunt trauma pain, any assessment conducted in the following 6 h will be replaced by the corresponding assessment done at the time of rescue.
- If a patient assesses spontaneous pain intensity and spontaneous pain relief at the time of rescue taken for reason other than blunt trauma pain, any assessment conducted in the following 6 h will be imputed as if the assessment were missed.
- If there are no assessments in the 12-24 h window, or the 24-48 h window,
 - if the patient has not prematurely terminated, a value from the last preceding assessment or assessment window will be carried forward.
 - $\circ~$ if the patient has prematurely terminated, imputation will proceed as described for assessments at the site.
- If the patient provides no post-baseline efficacy data, imputation will be considered in the Blind Review Meeting.

A Blind Review Meeting will take place before unblinding the randomization code. Handling of missing values/censoring/discontinuation, if necessary, will be provided and discussed in the Blind Review Meeting. Additional data handling rules will be specified in the BRM minutes to cover issues not anticipated in the above stipulations.

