Fresh impact injuries usually resolve spontaneously, but may nevertheless cause considerable discomfort, marked functional limitation, absence from work and withdrawal from activities [Inklaar 1994]. The goal of therapy is to minimize hemorrhage and inflammation and control pain. NSAIDs are commonly used to reduce pain and inflammation in order to facilitate rehabilitation and achieve earlier recovery [Dreiser 1993, Ekman 2002].

The efficacy and safety of topical NSAIDs in the treatment of acute, painful musculoskeletal conditions is widely recognized [Mason 2004, Rainsford 2008, Zacher 2008]. Over the past 20 years, an increasing number of topical NSAID formulations (diclofenac, ibuprofen, indomethacin, ketoprofen, and naproxen) have been approved. Topical NSAIDs, regardless of the status of the clinical condition (acute or chronic), must be applied at regular intervals in order to obtain maximum therapeutic benefit. A topical NSAID formulation is therefore not intended to be applied as needed and so is distinct in its mode of use when compared to that of oral NSAIDs.

Bioavailability studies suggest systemic absorption from topically applied NSAIDs is only 3-5% of the total systemic absorption achieved with oral administration [Heyneman 2000]. Pharmacokinetic data have shown that diclofenac, when applied topically, penetrates the skin barrier to reach joints, muscles and synovial fluid, in sufficiently high concentration to exert local therapeutic activity [Zacher 2008]. Further advantages of topical delivery include circumventing the gastrointestinal tract and avoiding first-pass metabolism in the liver.

Esflurbiprofen was approved by Pharmaceuticals and Medical Devices Agency of Japan (PMDA) on Sep 28, 2015. Esflurbiprofen is a cyclooxygenase (COX) inhibitor indicated for the treatment of osteoarthritis pain and inflammation.

Confidential Final Version 3.0

Esflurbiprofen is available on the Japanese market as a patch formulation, containing 40 mg of the active principle.

2 Purpose and rationale

Oral non-steroidal anti-inflammatory drugs (NSAIDs) are well known to reduce pain and inflammation and improve physical function [Ogilvie-Harris 1995]. However, due to their systemic availability they can cause intolerable and potentially life-threatening side effects, such as gastrointestinal symptoms (upset stomach, ulceration, hemorrhagic ulceration), alteration of platelet function, impairment of renal function, and interaction with other agents.

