6 SAMPLE SIZE

The calculation of 90 per treatment group is based on the following assumptions and considerations:

- Primary efficacy outcome is the change from baseline for POM at 72 hours after initiating treatment.
- Two-sided t-test situation with $\alpha = 5\%$.
- Assuming SD = 20 mm, the sample size provides approximately 80% power to detect a difference of 10 mm between two treatment groups if 64 patients per group are analysed.
- However, the sample size will be stipulated to n=90 per group in order to power also the two subgroup comparisons.
- Moreover, the sample size will be a total of 200 patients because a dropout-rate of approximately 10 % is taken into account.

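### After early stopping, missing 72 h pain is filled by LOCF in the primary analysis, and no missing-data sensitivity analysis is planned

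*SAP*

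**What the plan says.** SAP section 14.8 fills gaps by single imputation, with the rule set by the reason.

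- **Early stopping, general rule:** "all subsequent visits will be imputed by carrying the last non-missing observation forward". Protocol section 9.7.3 has the same rule.
- **Early stopping, exceptions:** the baseline value is carried forward after a suspected drug-related adverse event, and the worst documented value is used after lack of efficacy.
- **Missed visit (Visits 2 to 6):** "they will be imputed as the average of the preceding and the following assessments", with fractions rounded down.
- **No post-baseline data:** left to the Blind Review Meeting.

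The primary analysis (SAP 14.4.1) is an ANCOVA of the change to 72 h in the FAS. It makes no allowance for some values being imputed. The one analysis called a sensitivity analysis (SAP 5.1.2 and 14.4.3) is optional and concerns rescue medication. The per-protocol set (SAP 14.2) requires a 72 h efficacy value, but also an adhesion score of 0 to 2, no pain medication and no major violation.

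On the course of pain, Protocol section 1 says "Fresh impact injuries usually resolve spontaneously". Neither document gives mean pain by visit or expected dropout by arm.

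**The concern.** If pain is falling, a score taken at 12 or 24 h overstates the patient's likely pain at 72 h. LOCF then adds the missed fall to the mean of whichever arm lost the patient. When the two arms lose different shares of patients to LOCF, or patients with different falls still to come, the difference appears in the primary contrast as a treatment effect. It can favour either arm.

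This matters because SAP 14.4.1 sets a numeric target: the adjusted difference should exceed 10 mm. A shift of 1 to 3 mm is large against that. Because the filled values count as measured and no second method is planned, the report could not show how far the result depends on the rule.

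A smaller, separate matter is that the averaging rule ignores the unequal spacing of visits.

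**Working it through.** **Inputs from the SAP.** Section 6: "Two-sided t-test situation with" α = 5%; "Assuming SD = 20 mm"; 10 mm difference; 64 per group, raised to 90; about 10% dropout, 200 in total. Section 3: visits at 0, 12, 24, 48, 72, 96 and 168 h.

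**Assumed inputs.** p = share of an arm filled by LOCF. g = mean fall in POM from the last observed visit to 72 h. e = treatment effect already present at the last visit. Correlations between visits are also assumed.

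**1. The plan's own figure.** Normal approximation: n = 2 × (1.960 + 0.842)² × 20² / 10² = 62.8, so 63 per group. The exact t calculation gives 64 per group with power 80.15%, matching "approximately 80% power to detect a difference of 10 mm between two treatment groups" "if 64 patients per group are analysed". At 90 per group, power is 91.6%. Dropout: 90 / 0.90 = 100 per arm. The figure reproduces, but allows only for lost numbers, not for bias.

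**2. Shift with no true effect.** Shift towards the active patch = p_placebo × g_placebo − p_active × g_active. With the same g in both arms (mm):

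| Dropout active/placebo | g = 5 | g = 15 | g = 30 |
|---|---|---|---|
| 10% / 10% | 0 | 0 | 0 |
| 8% / 12% | 0.2 | 0.6 | 1.2 |
| 5% / 15% | 0.5 | 1.5 | 3.0 |
| 2% / 18% | 0.8 | 2.4 | 4.8 |
| 15% / 5% | −0.5 | −1.5 | −3.0 |

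**3. Type I error.** Simulation of a simplified ANCOVA (treatment and baseline only), 100 per arm, SD 20 mm at 72 h, dropout unrelated to outcome. Assumed mean POM is 70, 58 and 32 mm at 0, 24 and 72 h, with the last value at 24 h, so g = 26.

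- 10%/10%: no shift, about 5%.
- 3%/8%: 0.05 × 26 = 1.3 mm, about 7%.
- 4%/14%: 0.10 × 26 = 2.6 mm, about 15%. With g = 15: 1.5 mm, about 9%.
- 4%/14% with the last value at 48 h (assumed mean 42 mm, g = 10): 1.0 mm, about 7%.

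In similar simulations (72 h falls of 25–35 mm), analysing only observed 72 h values under the same dropout gave about 0 mm and 4.3–5.7%.

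**4. Shift with a true 10 mm effect.** The active arm now misses g + (10 − e).

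- Equal 10% dropout: 10 − 0.10 × (10 − e), which is 9.0 mm at e = 0 and 9.6 mm at e = 6.
- 14% active, 6% placebo, g = 26, e = 6: 0.06 × 26 − 0.14 × 30 = −2.64, so 7.4 mm. Simulated power is about 71%.
- The reverse split: 0.14 × 26 − 0.06 × 30 = +1.84, so 11.8 mm.

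**5. The averaging rule.** The correct linear weight on the preceding visit is (next − target) / (next − preceding).

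- Visit 5: (96 − 72) / (96 − 48) = 0.50. The plain average is exact linear interpolation.
- Visit 3: (48 − 24) / (48 − 12) = 0.67. The plain average is a value for (12 + 48) / 2 = 30 h.
- Visit 6: (168 − 96) / (168 − 72) = 0.75. The plain average is a value for (72 + 168) / 2 = 120 h.

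Rounding down costs at most 0.5 mm per filled value if the VAS is read in whole mm. With 10% filled, that is 0.05 mm on an arm mean, in the same direction in both arms.

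**The case against.** The other side has real points.

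- **LOCF does not cover every dropout.** Lack of efficacy and drug-related events, the reasons most likely to differ by arm, have their own rules. A 10-point gap must come from the remaining reasons, in a double-blind trial with matched patches. This stands, and makes the larger splits less likely. The two special rules are also single imputations and can shift the contrast in the same way.
- **Later data may exist.** Protocol 6.5.9 asks for the final evaluations within a week of stopping, and SAP 14.2 maps visits to the nearest target time. Some early stoppers may have a value at or after 72 h, so the share filled by LOCF could be well below 10%. This stands.
- **An analysis on observed 72 h data is planned.** A reader might infer that the FAS result has no check at all, and the per-protocol set shows otherwise. But it is selected on events after randomization, including pain medication use, so it does not test the FAS missing-data assumption.
- **LOCF does not always inflate type I error.** A reader might infer that it does. With equal dropout and no effect it stays near 5%.
- **The steep fall is not documented.** The protocol expects improvement but gives no rate. Entry needs at least 50 mm and a responder a 50% fall, so a responder falls at least 25 mm. That says nothing about the mean.
- **Averaging and rounding.** A reader might infer that these also bias the primary endpoint. They do not materially do so when Visits 4 and 6 are observed.

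SAP 14.8 also says that missing Visit 5 assessments are not imputed. That sentence concerns global assessments, so it should not be read as exempting POM. Its scope should be made explicit.

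**Conclusion.** The point holds in limited form. For patients who stop early for reasons other than lack of efficacy or a suspected drug-related event, the FAS primary analysis treats a carried-forward score as a measured 72 h score, and nothing planned tests that choice in the FAS.

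The size depends on quantities the documents do not give. It ranges from nothing (equal dropout, no effect) to 3.0 mm at 5% versus 15% dropout, in either direction. Error inflation is conditional on unequal dropout. Dilution under equal 10% dropout is 0.4 to 1.0 mm of a true 10 mm, which is modest. Whether the primary method itself must change is a matter of judgement in a phase II proof-of-concept trial; the absence of a sensitivity analysis is the firmer fault.

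The spacing error at Visits 3 and 6 is real but affects only secondary POM, AUC and SPID results, which are exploratory.

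**What to change.** SAP section 1 says the plan is finalized after the blind review meeting, so these changes can be made before unblinding.

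1. For the FAS primary endpoint, pre-specify multiple imputation of missing 72 h POM not covered by the reason-specific rules. Impute by arm, using baseline, all observed POM visits, center and subgroup, and pool by Rubin's rules. At minimum make this a sensitivity analysis; preferably make it primary and keep LOCF as the sensitivity analysis.
2. Interpolate by time for single missed visits: V3 = 2/3 V2 + 1/3 V4 and V6 = 0.75 V5 + 0.25 V7. Visit 5 needs no change when Visits 4 and 6 are observed.
3. Do not round VAS values.
4. State that the Visit 5 sentence in section 14.8 concerns global assessments only, if that is the intent.

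The cost is SAP text and modest programming, with no new data collection. The downside is slightly wider intervals, which reflect the uncertainty that single imputation hides.
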